5.2.2 Secondary and Exploratory Outcome Variables (if applicable)

We will determine if ‘asymptomatic’ SARS-CoV-2 positive subjects experience a partial or transitory loss of smell (hyposmia) and if so determine the fraction of subjects in which this occurs. Sensitivity, specificity and accuracy will be measured.

5.3 Study Population

This study is oriented towards the average US adult population and is limited to anyone over 18 years old (and excludes pregnant women). The goal is to be wide reaching and minimize selection bias of choosing outpatients. The study will focus on two cohorts: ‘drive-thru’ outpatients with minor COVID-19 symptoms (enough to merit a test) and healthy volunteer asymptomatic adults at high-risk of being infected with coronavirus. We will exclude pregnant women, those with pre-existing anosmia, head injury, scent allergies, asthma or a self-reported stuffy/runny nose. These conditions will be identified by patient self-report.

We will also exclude vulnerable patients with dementia as they are less likely to understand the test. They will be identified by asking if they usually make their own decisions about their medical care and sign for themselves; if not, then they would be excluded.

5.3.1 Number of Participants

Upon consultation with Yale biostatisticians Profs. [name] and [name], based on our sampling they calculated the following table to show the precision of sensitivity/specificity measurements for different sample sizes (**Table 1**). For example, the 95% confidence interval for 90% sensitivity with 100 subjects ranges from 82 to 95% , but if we have 400 subjects, the confidence interval ranges from 87 to 93% (about +/- 3%). Thus the number of participants will be guided by statistical analysis of the data. A minimal estimate is ~100 outpatients that are SARS-Co-V2 positive so as to have good confidence

intervals. Here we presume to have at least 100 age/gender matched SARS-Co-V2 negative subjects. If there are 3:1 SARS-Co-V2 negative to SARS-Co-V2 positive then ~400 outpatients (300 +100) will be tested. For the more exploratory testing with asymptomatics

Sens/Spec	Sample Size for Denominator*						
	100	150	200	250	300	350	400
0.50	0.20	0.17	0.14	0.13	0.12	0.11	0.10
0.60	0.20	0.16	0.14	0.13	0.11	0.11	0.10
0.70	0.19	0.15	0.13	0.12	0.11	0.10	0.09
0.80	0.17	0.13	0.12	0.10	0.09	0.09	0.08
0.90	0.13	0.10	0.09	0.08	0.07	0.07	0.06

we will limit the study to ~100 COVID-19 positive subjects and a similar number of SARS-Co-V2 negative subjects.

Table 1: Sample Size Calculations (Width of a 95% confidence interval around the proportion).

*Denominator is those that are COVID+ for sensitivity and those that are COVID- for specificity

5.3.2 Eligibility Criteria/Vulnerable Populations

Inclusion: In order to be eligible to participate in this study, an individual must meet all of the following criteria:

1. Provision of signed and dated informed consent form
2. Stated willingness to comply with all study procedures and availability for the duration of the study
3. Male or female, aged 18 or greater
4. Have a corresponding PCR test for SARS-CoV-2 on the same day.

Exclusion: An individual who meets any of the following criteria in either study population will be excluded from participation in this study (as this may cause unnecessary risk to the test subject or confound the results if the subject has pre-existing anosmia).

1. Adults unable to consent
2. Individuals who are not yet adults (infants, children, teenagers)
3. Pregnant women
4. Individuals with allergic to fragrances
5. Asthmatics

6. Patients with known neurocognitive disorders: dementia, Alzheimer's disease, Parkinson's disease
7. Adults with Acute or Chronic rhinosinusitis (They will be asked if they have a 'stuffy or runny nose'; they may be included in some tests, but their analysis would be segregated as they may be false positives due to allergies or a common cold or flu)

6 Methods

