6.1.2 Device Administration and Schedule

The device requires minimal preparation. The only key aspect is to not inadvertently damage it and as such would be given in a sealed pouch with a ‘golf pencil’, consent form, instructions and multiple choice answer sheet.

Patients who are in queue for drive-through COVID-19 testing will be approached by a research team member. No prior medical information will be provided to the study team regarding a patient’s eligibility.

The device in a pouch would be given to drive up outpatients that are undergoing PCR testing for COVID. Typically, the device packet would be placed on the test subject’s windshield just as they drive in and are waiting. If the subject consents to take the test, it will only take a minute. They will have the smell test and consent form digitally recorded (by camera) as they hold the test answers against the closed windows while inside the car. They will then give a nasal or oral sample for PCR testing, which is not conducted as part of the study. Of note, the subjects are already undergoing PCR testing and the smell study merely piggybacks on this other scheduled test. Thus there is practically no extra burden.

For the asymptomatic test the same protocol will be used, with the only minor difference is that the test can be replicated multiple times with different variants. As these tests are done in presence of a HCW there is little issue of compliance.

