7.1 Ethical Considerations: Informed Consent/Accent and HIPAA Authorization

The study will be conducted in accordance with the ethical principles that have their origin in the Declaration of Helsinki. No deception will be involved and there is no payment to participants. Only the minimal data necessary to complete the study will be obtained and age information will be binned help blind it. No direct subject indicators will be listed.

It is conceivable that potential new observation of anosmia in SARS-CoV-2 negative patients, may suggest a possible underlying condition, such as Alzheimer's or Parkinson's Disease (or head trauma), which may merit further testing by more in-depth tests. If so the olfactory test may be added to the record. The data will be flagged in EPIC for potential follow up and consideration by the patient's primary physician. The PI of the clinical trial team is **[name], MD who is a Yale Associate Professor of Rhinology and Endoscopic Skull Base Surgery** and is Yale's expert in olfaction and he could be consulted about the most appropriate follow up.

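### Exclusion 6 bars known Alzheimer's and Parkinson's disease, but no stated screening question, data field or analysis rule carries it out, so self-consenting patients can enter and may slightly bias specificity

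*Combined protocol and SAP*

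**What the plan says.** Protocol section 5.3.2, exclusion 6, removes from either study population "Patients with known neurocognitive disorders: dementia, Alzheimer's disease, Parkinson's disease". The introduction to the exclusion list gives two reasons for excluding: unnecessary risk, and factors that may "confound the results if the subject has pre-existing anosmia".

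Section 5.3 deals with part of this group in different terms: "We will also exclude vulnerable patients with dementia as they are less likely to understand the test". It then says how: "They will be identified by asking if they usually make their own decisions about their medical care and sign for themselves". Parkinson's disease is not named there. The same section lists other exclusions, including "those with pre-existing anosmia, head injury, scent allergies, asthma or a self-reported stuffy/runny nose. These conditions will be identified by patient self-report". Section 5.1 repeats that list as the preselection for outpatients and mentions no neurological disorder.

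On what the team can know, section 6.1.2 states "No prior medical information will be provided to the study team regarding a" patient's eligibility. Section 6.3.3 repeats this and says no further screening is needed. Section 7.3 limits record review to age, gender and the COVID result.

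Section 7.1 says that newly observed anosmia in a PCR-negative patient "may suggest a possible underlying condition, such as Alzheimer's or Parkinson's Disease (or head trauma), which may merit further testing by more in-depth tests".

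**The concern.** The stated screen and the exclusion select different people. A person with known Parkinson's disease, or early Alzheimer's disease, who handles their own medical decisions is excluded by 5.3.2 but passes the question in 5.3. That question concerns capacity; it does not ask about a diagnosis.

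The protocol itself links these diseases to smell loss, in section 7.1 and in section 2.1.1, which describes the use of smell tests in them. An affected person may fail the card whatever their infection status. If PCR-negative, they count as a false positive. If PCR-positive, they count as a true positive for a reason unrelated to the virus.

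The comparison with the CDC question is also exposed. Someone with long-standing loss can truthfully deny a new loss and still fail the card. Among PCR-negatives that counts against the card alone. Among PCR-positives it counts for the card alone, and resembles the under-reporting that section 6.1.1 hopes to demonstrate.

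**Working it through.** **1. Is there another point at which exclusion 6 could be applied?**

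- Answer form (6.3, step 2): five smell items, then questions on new loss, on changed smells over the past year, and on a stuffy or runny nose. Sites outside EPIC add gender and age band. There is no diagnosis item.
- Data table (6.3, step 4): no neurological field.
- Main-analysis exclusions (6.3, step 5; 6.4.5): stuffy nose, inconclusive PCR, and missing olfactory data. The answer on changed smells over the past year is recorded, but no rule uses it.
- Records (6.1.2, 6.3.3, 7.3): no prior medical information, and a review limited to three elements.

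No documented step after enrolment would reveal the diagnosis, so the analysts cannot repair the gap later.

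**2. The plan's own precision figures.** Sections 5.3.1 and 6.4.2 give an interval of 82-95% for 90% with 100 subjects, and 87-93% with 400. Exact (Clopper-Pearson) intervals reproduce both: 82.4-95.1% for 90/100 and 86.6-92.8% for 360/400. For 270/300, matching the 300 negatives in the plan's 3:1 example, the interval is 86.0-93.2%.

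**3. Size of the bias.** Let p be the share of PCR-negatives with known disease and f their probability of failing the card. Neither is in the documents, so both are assumptions, as is a specificity of 90% in unaffected negatives.

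Observed specificity = (1 − p) × 0.90 + p × (1 − f), so the loss is p × (f − 0.10).

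| p | f = 0.60 | f = 0.90 | Loss (points) |
|---|---|---|---|
| 1% | 89.5% | 89.2% | 0.5-0.8 |
| 2% | 89.0% | 88.4% | 1.0-1.6 |
| 5% | 87.5% | 86.0% | 2.5-4.0 |
| 10% | 85.0% | 82.0% | 5.0-8.0 |

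With f widened to 50-95%, the loss at 1-2% is 0.4 to 1.7 points. In counts, 300 negatives with a 1-2% share contain 3 to 6 affected people and yield 300 × 0.005 = 1.5 to 300 × 0.016 = 4.8 extra false positives on average.

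The exact interval's half-width is about 6.4 points with 100 negatives (width 12.7) and 3.6 with 300 (width 7.1). The loss at 1-2% is well inside both. It is a bias, however, so it does not shrink as more subjects are enrolled.

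**4. Sensitivity.** The change is p × (f − sensitivity). At p = 2% and f = 60-90%, it is 0 to +0.6 points if true sensitivity is 60%, and −0.6 to 0 if it is 90%. The direction is not fixed and the size is small.

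**The case against.** Exclusion 6 remains in force. Section 6.1.3 tests those who meet the criteria, and section 6.3.4 considers only eligible, consenting patients. Nothing in 5.3 permits enrolling someone whom 5.3.2 bars. A reader might infer that the protocol holds two rival definitions of one exclusion. The text does not support that: 5.3 addresses dementia and comprehension, and the list in 5.1 is a summary that also omits age. What is missing is a way to ascertain exclusion 6.

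The capacity question is not the only barrier. Self-reported pre-existing anosmia is excluded in 5.1 and 5.3, which removes patients who know of their loss. This safeguard is real but partial. The form has no item for it, and the protocol argues in 2.1.2 and 6.1.1 that people judge their own smell loss poorly, although it speaks there of acute or COVID-related loss.

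The form also lacks items for pregnancy, asthma and scent allergy, so it is evidently not the eligibility checklist. The consent form may list the exclusions; it was not available, and its content cannot be held against the plan. For those other conditions, however, the protocol at least names self-report as the method. For Alzheimer's and Parkinson's disease it names none.

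Finally, a reader might infer that such patients certainly enter and count as failures. They would have to sign for themselves, not disclose the diagnosis or any prior smell loss, and score below a cutoff not yet fixed. They can enter and may fail; the text supports no more.

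**Conclusion.** The point stands as a small, inexpensive improvement. The stated screen does not carry out exclusion 6 for people with known Parkinson's or early Alzheimer's disease who consent for themselves, and neither the data nor the analysis rules would reveal them.

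On the assumptions above, a 1-2% share costs about 0.5 to 1.6 points of specificity, with a slight distortion of the comparison with the new-loss question. For drive-through outpatients, who carry the primary outcome, and for working staff, this is minor.

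A reader might infer from the 5% and 10% rows that the primary result is in danger. The documents do not support that. They give no prevalence, the primary analysis is in outpatients, and the asymptomatic cohort is described as healthy volunteers (5.3) and health care workers (6.4.2, 6.4.3.2). Only section 5.1.1, which speaks of asymptomatic positive people as well as staff at a nursing home, hints at residents. If residents are enrolled, the effect in that secondary cohort could be larger.

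**What to change.** - Add one self-report item to the form in section 6.3, step 2, asking whether the person has been told they have dementia, Alzheimer's disease or Parkinson's disease (Yes/No). Add the matching field to the step 4 table.
- Apply exclusion 6 on that answer. Keep the decision-making question for capacity to consent.
- In step 5, leave anyone identified after testing out of the main analysis and report them separately, as is already planned for a stuffy nose.
- Reconcile sections 5.1, 5.3 and 5.3.2 so that they name the same conditions and the same way of identifying them.

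The cost is one tick-box, one data field, a wording alignment and a few subjects fewer in the main analysis. No sample-size figure changes. The item still relies on self-report, but it asks about a diagnosis the person has been given, so it does not depend on their noticing a loss of smell.

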5.1 General Design Description

This is a non-therapeutic correlative trial. Loss of smell in test subjects will be compared to the presence of SARS-CoV-2 coronavirus and statistically measured.

The study will focus on two cohorts: 'drive-thru' outpatients within the Yale New Haven Health System and in Central Louisiana and people at high-risk of being infected with coronavirus (New Canaan and Florida nursing homes) These sites are chosen as they have a significant incidence of COVID-19, they have on-going PCR testing, and they will provide support staff with experts in ENT to implement these studies.

The tests are double blinded as neither the subject or administering staff/doctor will know the results. The COVID-19 outpatients will be randomly recruited with the only preselection being the elimination of pregnant women, those with pre-existing anosmia, head injury, scent allergies, asthma or a self-reported stuffy/runny nose. These conditions will be identified by patient self-report.

The key features of the study design are:

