6.1.3 Method of Assignment/Randomization (if applicable)

All drive-through subjects that meet the inclusion/exclusion requirements will be tested.

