 - a. [Alternative should there be any issues with the camera or the patient must get out of the car]: The patient will take the completed test packet, place it back in the pouch and under the windshield. The HCW will take the packet and remove the **Consent Form** and **Multiple choice questionnaire form**, check if it is completed (if ask the patient), and place all remaining materials in a biohazard box for destruction. The Consent form and the Questionnaire will be digitalized (scan or photographed) and linked with EPIC so as to be compared to the PCR test results.
4. Information from the uploaded and **Multiple choice questionnaire form** will be entered by a person authorized to access the information into a table that includes:
 - a. Unique identifier
 - b. Gender
 - c. Age band (10 year)
 - d. Y/N to patient self-identified new loss of smell or taste
 - e. Y/N to patient response to "things in the last year smell different"
 - f. Y/N to patient self-identified blocked or stuff nose
 - g. Individual answers on the 5 window smell test
 - h. RT-PCR results for SARS-CoV-2 (+, - or Inconclusive)
 - i. Any other tests for COVID19 (CT or Serological) if given
5. The data will be analyzed in the following fashion:
 - a. Patients that report a blocked or stuffy nose will be excluded from the main analysis (as COVID-19 loss of smell is not due to nasal congestion); but will be analyzed separately to see how this would confound any interpretation.
 - b. Patients that are denoted SARS-CoV-2 "inconclusive" will be excluded from the main analysis; but will be separately analyzed to see if they colocalize with normosmia or anosmia.
 - c. Patients will be split into SARS-CoV-2 positive and negative. As the negative pool is likely to be much larger it will be statistically matched by gender and age profile (potentially with larger bands – e.g. 20 year, depending on the sample size)

- d. The + and - SARS-CoV-2 groups individual performance on the smell test (score 0-5) will be plotted as a histogram. A cutoff will best be chosen to segregate people with normosmia and anosmia (e.g. score = 2 or 3).
- e. False Positives (FP) and False Negatives (FN) will be identified and used to measure the selectivity and sensitivity, respectfully.
- f. Based on the statistical performance (see Table 1) we will determine when we have enough patients to complete the study with a given value of precision.

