6.4.3.5 Health economic evaluation

We will analyze how much the projected cost would be to test every American in the US with different cost models of the device (e.g. \$1 Unit) as compared to PCR based tests and current costs. We will then estimate based on the sensitivity and projected prevalence of Coronavirus, and current testing with PCR, the number of new cases that might be identified if taken to full scale, and the number that would be missed. This would provide a generalized estimated range given the underlying assumptions of the cost/benefit of wide-level screening with the olfactory device. Importantly unlike PCR tests this test could be rapidly scaled up by orders of magnitude. Also the test can be performed at home with only the test device and a cell phone. Because of this potential huge upside, we believe that it is critical to validate or invalidate the device as soon as possible

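### Stuffy or runny nose is both an entry exclusion and an enrolled, separately analysed group, so main specificity covers only people without nasal symptoms while the intended use has no such limit

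*Combined protocol and SAP*

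**What the plan says.** The protocol deals with nasal symptoms in five places.

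- Section 5.1 describes recruitment with "the only preselection being the elimination of pregnant women, those with pre-existing anosmia, head injury, scent allergies, asthma or a self-reported stuffy/runny nose".
- Section 5.3 repeats the rule: "We will exclude pregnant women, those with pre-existing anosmia, head injury, scent allergies, asthma or a self-reported stuffy/runny nose".
- Section 5.3.2 opens its list by saying that anyone meeting a listed criterion "will be excluded from participation in this study". Item 7 of that list is acute or chronic rhinosinusitis, checked by asking about a stuffy or runny nose. The same item then says "they may be included in some tests, but their analysis would be segregated as they may be false positives due to allergies", and goes on to name colds and flu.
- Section 6.1.3 says "All drive-through subjects that meet the inclusion/exclusion requirements will be tested".
- Section 6.3 puts the nose question on the answer form, which is completed after consent. Step 5a then says "Patients that report a blocked or stuffy nose will be excluded from the main analysis", followed by a separate analysis to see how far nasal symptoms confound the reading.

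On use, section 3.2 foresees broad deployment as a first indicator with PCR confirmation, and section 6.1.1 foresees wide-scale US testing. Neither limits use to people without nasal symptoms. Section 5.3 aims the study at ordinary US adults and wants to keep selection bias low. No estimate that pools people with and without nasal symptoms is planned.

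**The concern.** There are two linked problems.

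First, a person who answers Yes to the nose question is ineligible under sections 5.1 and 5.3 and the lead-in of 5.3.2, but belongs to a planned analysis group under item 7 and step 5a. If the entry rule is applied as written, step 5a has nobody to analyse.

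Second, the reason given for setting this group apart is that its members may test falsely positive. Taking likely false positives out of the PCR-negative denominator raises specificity. The resulting figure is sound for people without nasal symptoms, but the intended use is wider. The outpatient cohort consists of people with symptoms mild enough for a drive-through visit, so nasal complaints among PCR-negatives are plausible. Section 3.2 leaves the device's false-positive rate to be filled in by this study, beside a PCR figure of under 5%. A rate from the restricted group would be read there as the rate for everyone.

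**Working it through.** **1. The plan's own precision figures.** Sections 5.3.1 and 6.4.2 give, for a proportion of 90%, a 95% interval of 82 to 95% at n=100 and 87 to 93% at n=400. Table 1 gives widths of 0.13 and 0.06. Exact (Clopper-Pearson) intervals are 82.4 to 95.1% (width 0.127) and 86.6 to 92.8% (width 0.061). They reproduce the plan, and at n=300 the width is 0.071 against 0.07 in the table. The precision figures are not in error.

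**2. Specificity in all enrolled subjects.** Let s be the share of PCR-negatives with a stuffy or runny nose, and f the share of those who fail the card. Then

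Sp(all) = (1 - s) x Sp(clear) + s x (1 - f).

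Sp(clear) is set to 0.90, a row of Table 1. The documents give neither s nor f, so both are assumptions: s from 10 to 40%, f from 20 to 50%.

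| s | f | Calculation | Sp(all) | Drop from 0.90 |
|---|---|---|---|---|
| 0.10 | 0.20 | 0.90 x 0.90 + 0.10 x 0.80 | 0.89 | 1 point |
| 0.20 | 0.30 | 0.80 x 0.90 + 0.20 x 0.70 | 0.86 | 4 points |
| 0.20 | 0.40 | 0.80 x 0.90 + 0.20 x 0.60 | 0.84 | 6 points |
| 0.40 | 0.50 | 0.60 x 0.90 + 0.40 x 0.50 | 0.74 | 16 points |

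The drop is zero only if s = 0 or if congested PCR-negatives fail no more often than others. The second would contradict item 7's reason for segregating them.

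**3. Scale against sampling error.** Half the Table 1 width at 0.90 is about 3.5 points at n=300 (0.07/2) and 6.5 points at n=100 (0.13/2). The 1-point drop lies inside both, the 4-point drop lies inside the second only, and the 16-point drop lies outside both.

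**4. Sensitivity and accuracy.** If congestion makes people fail the card, congested PCR-positives would also fail more often, so all-enrolled sensitivity could be higher than in the main analysis. With p the share of PCR-positives, held fixed, the change in accuracy is p x (change in sensitivity) + (1 - p) x (change in specificity). Take the 6-point drop in specificity. At the plan's 100 positives to 300 negatives (p = 0.25), it costs 0.75 x 6 = 4.5 points of accuracy, and sensitivity would have to rise by 4.5/0.25 = 18 points to offset it. At one-to-one matching (p = 0.5), it costs 3 points, offset by a rise of 6. The net effect on accuracy depends on the case mix.

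**5. Counts.** Neither sample size section makes an allowance for subjects removed at step 5a. If the planned 300 negatives and 100 positives include people with nasal symptoms and 10-40% are removed, 270 to 180 negatives and 90 to 60 positives remain. Exact widths at 0.90 then go from 0.071 to 0.075-0.093 for negatives, and from 0.127 to 0.135-0.167 for positives. Keeping 100 positives in the main analysis would need 100/0.9 to 100/0.6, that is 112 to 167 positives tested.

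**The case against.** The congestion-free analysis has an open scientific reason. Section 2.2 cites evidence that smell loss points to COVID-19 once nasal blockage is set aside. Step 5a promises to look at the other group, and if those people are enrolled, a pooled figure is simple arithmetic. Section 3.2 also sends card-positives to PCR, which limits the harm of a false positive. The drive-up procedure gives everyone the packet and asks the nose question on the form, and section 6.3.3 wants no further screening, so practice probably leans towards enrolment. All of this stands. It supports keeping the step 5a analysis, but it does not reconcile the entry rules or supply an estimate for the stated use.

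A reader might infer more than the documents support:

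- *That the restricted specificity feeds the national projection.* Section 6.4.3.5 works from sensitivity, prevalence and current PCR testing. Its phrase "how much the projected cost would be to test every American in the US" concerns cost, and specificity is not a named input.
- *That every performance measure is biased in the device's favour.* The direction is supported for specificity only. Main-analysis sensitivity may be lower than in all enrolled subjects.
- *That even the smallest plausible shift exceeds the interval half-width.* That depends on the assumed floor and on n; step 3 of the working shows cases where it does not.
- *That the excluded trait changes because step 5a says blocked or stuffy.* The form has one nose item, so step 5a can act only on that answer. This is loose wording.
- *That sites will enrol different populations.* The text permits this but does not show it.

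**Conclusion.** The point holds in two parts. The contradiction over entry is plain from the text, and item 7 of section 5.3.2 conflicts with its own lead-in. Main specificity will describe people without nasal symptoms and, on the plan's own reasoning, will be favourable relative to an intended use that has no congestion limit. The size cannot be derived from the documents. Under the assumptions above it runs from 1 to 16 points, with 6 points in a middle case. The mismatch would disappear if the performance claim were limited to people without nasal symptoms, but the current text does not limit it. The plan should be changed before results are read against the intended use.

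**What to change.** - Reconcile sections 5.1, 5.3, 5.3.2 (lead-in and item 7), 6.1.3 and 6.3 so that people who answer Yes to the single stuffy-or-runny-nose item are enrolled and flagged, as step 5a already assumes. Use that item's wording in steps 4f and 5a. Say whether known rhinosinusitis, which item 7 names, is handled by the same flag.
- Keep the step 5a main analysis, label it as applying to people without nasal symptoms, and count the target of about 100 PCR-positives within it.
- Beside it, report sensitivity, specificity and accuracy in all enrolled subjects at the cutoff already chosen, without choosing a new one. State how the step 5c matching applies to this row; using the same rule for both keeps them comparable.
- Either base the intended-use statement on the all-enrolled row or limit the performance claim to people without nasal symptoms.

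Cost: wording in these sections and an added set of results, from an item already on the form. All-enrolled specificity will probably look less favourable, and somewhat more subjects may have to be tested to keep the main-analysis counts.
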